#### Study Procedures

##### *Subject Recruitment*

We plan to recruit all of our study subjects from the UMP Women's Health Specialists Clinic. During their routine office visit for their pregnancy the participating physician or their affiliated nurse will make those patients who meet the study inclusion criteria aware of this study and ask them if they would

be interesting in hearing more information about the clinical study. Those patients who express a willingness to listen to a description of the study, will have the purpose of and procedures involved explained to them. Each woman will be given an opportunity to ask questions and given time to consider whether they would like to participate. For those women who would like to participate, oral and written informed consent will be obtained. Consenting participants will then be randomly assigned to one of the two study arms.

*Study Data:*

Baseline data will include the following:

- Maternal age
- Race
- Parity
- Height
- Body weight
- BMI
- Weight gain during pregnancy
- Number of missing teeth
- Overall dental health
- Temporomandibular dysfunction: presence or absence
- Vitals

*Dental Visit:*

Women who consent to participate in the study and are randomized to the intervention arm of the study will be scheduled for a dental examination. Participants will be seen at the UMP Adult Dental Clinic or Clinics and Surgical Center dental clinic for a general dental exam. Subjects randomized to the interventional arm of the study will also have impressions for fabrication of an OSD. They will be scheduled for a return visit to have the OSD tried in and adjusted if necessary.

*Post Delivery Data:*

An obstetrical nurse will abstract additional pertinent maternal health and birth information from the subject's medical record during labor including:

Woman:

- Gestational age at delivery

- Estimated fetal weight
- Indications for induction
- Use of oxytocin in labor
- Obstetrical complications
- Obstetrical interventions with indications
- Time of Second Stage Labor
- Use of epidural
- Vitals

Neonate:

- Birth weight
- Apgar score
- Head circumference
- Admission to the NICU and indications

Additionally, all women in the interventional group will be given a satisfaction survey relative to their experience with the OSD:

- 1- Disliked or refused use
- 2- not helpful
- 3- fair
- 4- helpful
- 5- very helpful

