#### I.1.3.4. Statistical considerations.

##### *Statistical Analyses.*

The sample size is based on Aim 1. A sample size of 247 per group will have 90% power to detect a mean difference of 12 minutes between groups using a two group t-test at the 0.05 level of significance and assuming a standard deviation of 41.

For aim 2, this sample size of 247 per group will have 86% power to detect differences of a 1.2% Caesarean section rate in the OSD group and a 6.4% Caesarean section rate in the control group using a chi-square test at the 0.05 level of significance. For aim 3, 247 per group will have 90% power to detect a

mean difference in Apgar scores of 0.29 standard deviations using a two group t-test at the 0.05 level of significance.

Given that some patients will not reach second stage labor (e.g. Cesarean section prior to second stage labor), we plan to enroll additional patients to ensure that 247 patients per group reach the second stage of labor.

The planned statistical analyses are designed to address each specific aim. Descriptive statistics will be calculated for demographics, patient characteristics, and outcomes. The distributions and skewness of the continuous outcomes will be evaluated.

**Aim 1:** To determine if an OSD can reduce the duration of the second stage of labor

Mean duration of second stage labor will be compared between the OSD and control groups using a two group t-test. We will also explore the effect of important covariates (e.g. epidural or oxytocin use) on duration of second stage labor and whether this effect differs by group using linear regression models. Since some women will likely undergo a caesarean section or operative vaginal delivery during second stage labor, time from onset of second stage labor until delivery will be compared between groups using a log-rank test. Women undergoing these procedures will be censored.

**Aim 2:** To determine if an OSD can reduce the incidence of labor complications including Caesarian Sections

Rates of labor complications (including Caesarian Sections) will be compared between the OSD and control groups using chi-square tests or Fisher's exact tests. Similar to aim 1, we will also explore the effect of important covariates (e.g. epidural or oxytocin use) on rates of labor complications and whether this effect differs by group using logistic regression models.

**Aim 3:** To determine if the use of an OSD can improve Apgar scores in newborns.

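### The Aim 1 t-test is unadjusted although maternal age, height and BMI are collected before assignment; prespecifying them is a low-priority, probably small gain in precision

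*Combined protocol and SAP*

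**What the plan says.** Section I.1.3.4 sizes the trial on Aim 1: "A sample size of 247 per group will have 90% power to detect a mean difference of 12 minutes between groups", with a t-test at the 0.05 level and an SD of 41. The analysis follows the same form: "Mean duration of second stage labor will be compared between the OSD and control groups using a two group t-test".

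Regression appears only as exploration: "We will also explore the effect of important covariates (e.g. epidural or oxytocin use) on duration of second stage labor". The same sentence plans to check, by linear regression, for covariate effects that vary between the arms. The two covariates are given as examples, so the list is open. Oxytocin is among the items abstracted from the labor record ("Use of oxytocin in labor", Synopsis, Post Delivery Data), and so is epidural use.

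The Synopsis (Study Data) opens its list with "Baseline data will include the following". The list includes maternal age, height and BMI, as well as parity, weight gain during pregnancy and several dental items. Section I.1.3.1 says that assignment follows collection of baseline data. Under Dental Visit, women who are "randomized to the intervention arm of the study will be scheduled for a dental examination"; no such visit is described for controls.

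**The concern.** A covariate that is measured before assignment and predicts the outcome narrows the confidence interval for the treatment difference without adding patients. The plan collects three plausible candidates and leaves them out of the Aim 1 comparison. The covariates it does name are the wrong kind for adjusting the OSD effect: epidural and oxytocin use occur after assignment and could themselves be affected by the course of labor.

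Two things are at stake, both limited. Some precision may be forgone. And because the covariate list is open, an adjusted estimate specified after the data are seen would be post hoc, with no protection against choosing covariates by their effect on the result.

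**Working it through.** **Inputs from section I.1.3.4:** n = 247 per group, difference 12 minutes, SD 41, alpha 0.05. Sidedness is not stated; two-sided is used because it reproduces the stated n (a one-sided test would need about 200 per group).

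**Assumed input:** R², the share of variance in second-stage duration explained by age, height and BMI together. The documents do not give it, so 0, 2, 5, 10 and 20% are shown.

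**Step 1: reproduce the plan's figure.**
- Standard error of the difference = 41 × √(2/247) = 3.69 min.
- Noncentral-t power with 492 degrees of freedom = 90.1%. The sample size for 90% power is 246.3, rounded up to 247. The plan's figure is confirmed.
- 95% CI half-width = 1.965 × 3.69 = 7.25 min.

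**Step 2: adjust for p = 3 baseline covariates.**
- Residual SD = 41 × √(1 − R²).
- Estimating the covariate coefficients multiplies the variance by 1 + p/(2n − p − 3) = 1 + 3/488 = 1.0061.
- Degrees of freedom = 492 − 3 = 489.
- Equivalent n per arm = 247 / [(1 − R²) × 1.0061].

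Example at R² = 5%: residual SD = 41 × √0.95 = 39.96; standard error = 39.96 × √(2/247) × √1.0061 = 3.61 min; half-width = 1.965 × 3.607 = 7.09 min; equivalent n = 247 / (0.95 × 1.0061) = 258.4, about 11 more women per arm.

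| Assumed R² | Power at 247 per arm | CI half-width (min) | Equivalent change in women per arm |
|---|---|---|---|
| t-test, no adjustment | 90.1% | 7.25 | – |
| 0% | 89.9% | 7.27 | about −1.5 |
| 2% | 90.5% | 7.20 | about +3.5 |
| 5% | 91.3% | 7.09 | about +11 |
| 10% | 92.7% | 6.90 | about +26 |
| 20% | 95.1% | 6.50 | about +60 |

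**Step 3: break-even.** Setting (1 − R²) × 1.0061 = 1 gives R² = 1 − 1/1.0061, about 0.6%. Below that, adjustment costs slightly more than it returns.

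**Step 4: which listed baseline items can be used.**
- Maternal age, height and BMI at enrolment: usable.
- Parity: constant, because all women are nulliparous.
- Weight gain during pregnancy: not complete at assignment, since women enroll in any trimester (section I.1.3.1).
- Dental items: the examination is scheduled only for the intervention arm, so these may not be comparable between arms.

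**The case against.** The strongest reply is that this is a preference and not a defect. An unadjusted t-test matches the sample-size basis, the trial already has 90% power, and regression on important covariates is planned, with age, height and BMI unnamed but not excluded. That stands, and it is why the priority is low. It does not remove the case for naming the covariates in advance.

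A second reply is that the benefit rests on an R² that nobody has supplied. This also stands. At 2% the gain is 0.4 power points and 0.05 minutes of half-width; only at 10 to 20% is it easily visible, and nothing in the documents supports such values for these variables in nulliparous women with uncomplicated pregnancies. BMI measured in any trimester also partly reflects gestational age, which may weaken it as a predictor.

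A third is that the Synopsis describes assignment after consent without mentioning baseline collection, so the timing rests on section I.1.3.1. Age and height are unaffected.

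Two stronger readings are tempting. A reader might infer that the omission makes the Aim 1 analysis wrong or underpowered; the stated power reproduces, so the documents do not support that. A reader might also infer the reverse, that precision is the only thing left to improve in the t-test. The documents do not support that either: the comparison covers only women who reach second stage, a group formed after randomization. The plan censors cesarean and operative vaginal deliveries in its log-rank test but does not say how the t-test treats them.

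**Conclusion.** The point holds as a low-priority improvement. The Aim 1 t-test uses no covariates, three suitable ones are collected before assignment, and no model names them. Over an assumed R² of 2 to 20%, the net gain is 0.4 to 5.0 power points and 0.05 to 0.75 minutes of CI half-width. The worst case is a loss of about 0.2 power points if the covariates explain nothing. The gain is therefore likely but not certain, and its size cannot be fixed from the documents. The figures assume 247 women per arm in the analysis, the stated SD of 41 and a linear model with three covariates.

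Adjustment for age, height and BMI does not resolve the restriction to women who reach second stage or the unstated handling of procedures that end it. Those are separate matters and weigh more.

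**What to change.** In section I.1.3.4, Aim 1, state the following.

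1. The difference in mean second-stage duration and its 95% CI come from a linear model with arm, maternal age, height and BMI at enrolment. This is the deciding mean-duration analysis.
2. The unadjusted t-test is reported as supportive.
3. The OSD effect is not adjusted for epidural use, oxytocin use, weight gain during pregnancy, parity or the dental items. The exploratory epidural and oxytocin models are descriptive and do not estimate the OSD effect.

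The covariate set should be closed, with no examples or optional additions. The cost is SAP wording only: no new data, visits or patients, because all three variables are already on the baseline list.

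### Oxytocin use is listed without a start time, so its exploratory link to second-stage duration, and any difference in that link by group, could in part be reverse causation (minor)

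*Combined protocol and SAP*

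**What the plan says.** In I.1.3.4 (Statistical Analyses, Aim 1), the primary comparison of mean second-stage duration is an unadjusted two-sample t-test. The plan then adds: "We will also explore the effect of important covariates (e.g. epidural or oxytocin use) on duration of second stage labor", and asks "whether this effect differs by group using linear regression models". Aim 2 repeats the idea with logistic models: "Similar to aim 1, we will also explore the effect of important covariates (e.g. epidural or oxytocin use) on rates of labor complications".

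The data behind these models are listed in I.1.1 (Synopsis, Post Delivery Data), where a nurse is to "abstract additional pertinent maternal health and birth information from the subject's medical record during labor". The relevant items are "Use of oxytocin in labor" and "Use of epidural". Neither carries a start time, a stage of labor or a reason for starting. Two nearby items, "Indications for induction" and "Obstetrical interventions with indications", could hold some reasons, but neither names oxytocin or asks for timing. No section restricts the covariates to exposure that began before second stage.

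**The concern.** The outcome is a length of time, and the exposure can begin during that time. The longer a woman remains in second stage, the more opportunity there is for oxytocin to be started and recorded. This is so even if starts within second stage are random, and more so if slow progress prompts them. A use/non-use covariate for labor as a whole mixes these women with those whose oxytocin began earlier, and linear regression cannot tell the two directions apart.

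The by-group question adds a second route. The OSD is worn only in second stage. If it works, fewer OSD women stay undelivered long enough to be started late, so the oxytocin users differ in make-up between arms. A difference in the apparent oxytocin effect could then appear although oxytocin does nothing. At stake is how the exploratory results are read, in particular any suggestion that the OSD works differently with and without oxytocin.

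**Working it through.** **The plan's own figure.** Inputs from I.1.3.4: difference 12 min, SD 41, alpha 0.05 (two-sided assumed), 90% power. Normal approximation: n = 2(1.960 + 1.282)² × 41² / 12² = 245.3, so 246 per group. By the noncentral t, power is 89.97% at 246 and 90.1% at 247. The stated 247 reproduces and is not in dispute.

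**Assumptions for the check, none of which the documents give.** Control mean 60 min; lognormal durations with SD 41; OSD effect as a proportional cut of 12/60, giving a mean of 48; true oxytocin effect zero; a share e (30% or 50%) on oxytocin before second stage, unrelated to its length; a share q of the remaining women started once second stage passes 90 min.

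**Closed form for one arm.** Let p = P(duration > 90), m = mean duration among those women, M = arm mean, and a = (1 − e)qp, the fraction started late.
- Mean with oxytocin = (eM + am)/(e + a)
- Mean without = (M − eM − am)/(1 − e − a)
- False effect = the difference between them

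**Worked case, e = 0.3, q = 0.3.** Log-variance = ln(1 + (41/60)²) = 0.3832, so the log-SD is 0.619.
- Control: p = 0.1674, m = 130.78, a = 0.7 × 0.3 × 0.1674 = 0.03515. With oxytocin: (18 + 4.597)/0.33515 = 67.42. Without: (60 − 22.597)/0.66485 = 56.26. False effect +11.17 min.
- OSD: p = 0.0926, m = 124.48, a = 0.01945. With: (14.4 + 2.421)/0.31945 = 52.66. Without: (48 − 16.821)/0.68055 = 45.81. False effect about +6.84 min.
- False interaction: 6.84 − 11.17 = −4.33 min.

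**Simulation on the same assumptions** (247 per arm, 500 trials per row, true OSD effect −12 min):

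| Early use | Late-start share q | False oxytocin effect (min) | p < 0.05 | False interaction (min) | p < 0.05 |
|---|---|---|---|---|---|
| 30% | 0 | −0.3 | 4% | 0.0 | 5% |
| 30% | 10% | +3.0 | 15% | −1.5 | 5% |
| 30% | 30% | +9.2 | 74% | −4.9 | 11% |
| 30% | 50% | +14.7 | 99% | −6.6 | 18% |
| 50% | 0 | +0.1 | 5% | −0.3 | 5% |
| 50% | 10% | +1.8 | 8% | −1.0 | 6% |
| 50% | 30% | +5.5 | 40% | −2.6 | 5% |
| 50% | 50% | +9.4 | 81% | −4.4 | 10% |

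The false effect here comes from the model without interaction, so it lies between the two arm values. The closed form agrees with the simulation within simulation error.

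**Other settings.**
- Gamma durations, control mean 60 or 75, starts after 60 or 90 min, 30% early use, q = 25–50%: false effect +8.3 to +19.7 min; interaction −0.6 to −7.8 min.
- Across all simulations the false interaction is significant in 2–23% of trials.
- If the OSD has no effect, the interaction is about zero and rejection stays near 5%. The false oxytocin effect remains.
- Adjusted OSD effect: −11.6 against −12.1 unadjusted in the lognormal row with 30% early use and q = 50%; −11.1 to −11.9 in the gamma runs.
- Counting only oxytocin begun before second stage: coefficient and interaction both within about 0.4 min of zero.

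**The case against.** The strongest reply is that no planned conclusion rests on these models. The plan calls them exploratory, and the t-test, log-rank, chi-square or Fisher, and Apgar comparisons use no covariates. That stands, and it is why the point is minor.

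Several stronger readings are tempting and should be resisted:
- **That the oxytocin coefficient would be reverse causation.** The documents do not say when oxytocin is given or how often it starts late. Use for induction or in first stage precedes the outcome. At a 10% late-start share the lognormal artefact is only +1.8 to +3.0 min.
- **That the same holds for epidural.** Nothing in the documents suggests epidurals are placed because second stage is long. The item is untimed and arises after randomization, which justifies a precaution and no more.
- **That the plan records use strictly as yes or no.** The Synopsis gives a topic list, and the case-report forms are not shown. "Obstetrical interventions with indications" might capture some augmentation. The supportable statement is that timing is not specified.
- **That the adjusted OSD effect is badly biased.** The plan does not clearly promise one, and the shift is under 1 min.
- **That a spurious subgroup finding is likely.** The false interaction needs a working OSD and is usually not significant.

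**Conclusion.** The point holds as a minor one, for oxytocin. As documented, the item cannot separate oxytocin begun before second stage from oxytocin begun because second stage was long. The exploratory coefficient, and the by-group difference if the OSD works, could therefore in part reflect reverse causation. Under assumed late-start shares of 10–50% and no true oxytocin effect, the false effect is about +2 to +20 min, against the 12 min the trial is sized to detect. The false interaction is about −1 to −8 min.

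These sizes rest on the assumed control mean, duration distribution, early use and late-start share; only the SD of 41, the 12-minute difference and 247 per group come from the plan. With no late starts the bias is nil. A reader might infer that the trial's main result is at risk. It is not: the primary test is unadjusted, and the sample size and power stand.

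**What to change.** - **Post Delivery Data list (I.1.1):** record whether oxytocin was started before or during second stage, with clock time. Record epidural time as a low-cost precaution.
- **Aim 1 linear models (I.1.3.4):** use only exposure begun before onset of second stage. Report later starts descriptively by arm. Call the covariate results associations rather than effects, since neither covariate is randomized.
- **Aim 2 logistic models:** do not carry the second-stage rule over unless these models are limited to women who reach second stage. The plan expects some Cesareans before then, and for those women the split is undefined. Otherwise, simply describe the results as associations.

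The cost is a stage and time entry per item, from a labor record already being abstracted, and a sentence or two in the analysis section. The downside is slightly more abstraction work. Adding the fields now is easier than returning to about 500 charts later, because no analysis can recover timing that was never recorded.

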#### Secondary Obstetrical Outcomes

- Complications of Pregnancy (C-section)
- APGAR Score of Neonate

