#### **I.1.2. Background and Rationale**

- Importance

Prolonged labor, especially during the second stage of active expulsive effort (the pushing phase), is associated with increased risk of maternal complications (e.g. tissue trauma, postpartum hemorrhage, intra-amniotic infection). Developing an effective method to assist and maximize maternal expulsion effort should be of

great value in reducing the number of complications, also including cesarean section or instrumental deliveries. Past studies published in the dental literature have shown that specially designed oral appliances that support the dental occlusion may increase the isometric strength of different muscle groups. Increased strength of the neck muscles could improve efficiency of the Valsalva (pushing) maneuver in increasing intra-uterine pressure, and thus decreasing the duration of phase II of labor. It has also been shown that specially designed oral appliances can have an effect on neuro-endocrinology especially the Paraventricular nucleus of the hypothalamus and CRH levels, reducing cortisol levels in athletic stress. CRH having a role in the female reproductive system could be positively affected by the anti-stress properties of certain oral appliances.

- Improvement in scientific knowledge and clinical practice

This project could lead to an increased ability to determine when intervention during pregnancy utilizing an occlusal support device might decrease the incidence of caesarian section and other complications that occur during the second phase of labor.

- Changes based on this project if specific aims are achieved

If results are successful, routine clinical obstetrical care could include the fabrication of an OSD, thus utilizing a minimally invasive technique to positively impact the outcomes of labor.

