#### Secondary Obstetrical Outcomes

- Complications of Delivery
- APGAR Score of Neonate

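### Aim 2, a secondary aim, is analysed by an open-ended set of complication tests with no deciding test and no error control; name caesarean section, the only powered outcome, as that test

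*Combined protocol and SAP*

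**What the plan says.** The secondary complication outcome appears in two forms. The synopsis (I.1.1, Secondary Obstetrical Outcomes) gives "Complications of Pregnancy (C-section" with the bracket closing there, so caesarean section is the only item shown. Section I.1.3.2 gives "Complications of Delivery" and lists nothing under it.

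The Aim 2 analysis in I.1.3.4 reads "Rates of labor complications (including Caesarian Sections) will be compared between the OSD and control groups using chi-square tests", with Fisher's exact test as the alternative. Both the rates and the tests are plural, and caesarean section is included among them without being singled out.

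The power statement in the same section covers caesarean section only: "For aim 2, this sample size of 247 per group will have 86% power to detect differences of a 1.2% Caesarean section rate" with the device, set against 6.4% among controls, by a "chi-square test at the 0.05 level of significance". No level is given for any other complication, and no multiplicity rule, ranking or composite is defined.

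The data collected after delivery (I.1.1, Post Delivery Data) include obstetrical complications and interventions as general headings, without a list. The background (I.1.2) links prolonged labor to "increased risk of maternal complications (e.g. tissue trauma, postpartum hemorrhage, intra-amniotic infection" and, in the next sentence, adds caesarean and instrumental delivery.

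**The concern.** A single aim is to be answered by an unspecified number of tests. The list can be settled after the data are seen, and nothing says which result counts. A significant result on one unpowered complication could then be presented as showing that the OSD reduces labor complications, with the same standing as the powered caesarean comparison.

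This matters because Aim 2 is a numbered specific aim with its own power statement, and only its covariate models are described as exploratory. The background also says that success could bring the OSD into routine obstetrical care. The 0.05 level holds for one test; it does not hold for the aim as analysed.

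**Working it through.** **Inputs from the plan.** 247 per group; 1:1 allocation; caesarean rates 1.2% and 6.4%; level 0.05; stated power 86% (all I.1.3.4, except allocation, I.1.1 and I.1.3.1). The plan does not state whether tests are one-sided or two-sided.

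**Reproducing the 86%.** Normal approximation, pooled variance under the null:

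- Mean rate (0.012 + 0.064)/2 = 0.038.
- Null standard error √(2 × 0.038 × 0.962/247) = 0.01720.
- Alternative standard error √[(0.012 × 0.988 + 0.064 × 0.936)/247] = 0.01705.
- Two-sided power Φ[(0.052 − 1.96 × 0.01720)/0.01705] = Φ(1.07) = 85.8%.
- One-sided, with 1.645 in place of 1.96: 91.8%.

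The stated figure is therefore a two-sided 0.05 calculation for one test.

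**Error over k tests.** With no true effect and independent tests at two-sided 0.05, the chance of any significant result is 1 − 0.95^k, and of at least one favouring the OSD 1 − 0.975^k.

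| Tests | Any false result | Favouring the OSD |
|---|---|---|
| 1 | 5.0% | 2.5% |
| 4 | 18.5% | 9.6% |
| 5 | 22.6% | 11.9% |
| 10 | 40.1% | 22.4% |

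Five is the count mentioned in the background: tissue trauma, postpartum hemorrhage, intra-amniotic infection, caesarean section and instrumental delivery. It is an illustration, not a planned number.

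**Allowing for correlation and sparse tables.** The plan gives no rates for complications other than caesarean section and no correlations, so these are assumptions. Five complications were simulated with 247 per arm and no true effect, using chi-square with Fisher's exact test when an expected count is below 5, and latent correlation within a woman of 0 to 0.6.

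| Assumed rates | Any false result | Favouring the OSD |
|---|---|---|
| All five at 2% | about 15% to 16% | about 8% |
| 1%, 2%, 2%, 3%, 6.4% | about 16% to 17% | about 8% to 9% |
| Commoner events, up to 20% | about 20% to 23% | about 10% to 12% |

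**What lowers the figure.**

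- Fisher's test for all five, independent: 4.1% if every rate is 1%, 9.8% at 2%, 15.6% at 6.4%, 17.8% at 20%.
- Correlation between the five test statistics themselves: 18.3% at 0.5 and 12.7% at 0.8 (9.1% and 6.4% favouring the OSD).

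**Cost of the alternatives.** Bonferroni over five tests uses 0.05/5 = 0.01 each. Caesarean power is then Φ[(0.052 − 2.576 × 0.01720)/0.01705] = 67.4%. With caesarean section as the one deciding test, the level stays at 5% and the power at 86%.

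**The case against.** The strongest reply is that caesarean section is already the evident lead test. It is the only complication shown in the synopsis outcome list and the only one in the Aim 2 power statement. These are also secondary outcomes: the sample size rests on Aim 1, and no section promises familywise control over secondary outcomes or says that any single significant complication meets Aim 2. Whether such outcomes need formal control is partly a matter of judgement.

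Much of this stands. Caesarean section is the natural lead, which is why the fix costs so little. But it has to be inferred: the Aim 2 analysis text only includes it among other complications, and I.1.3.2 drops it from the outcome.

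A reader might go further and infer that the plan names five complications, tests each at 0.05, and so carries a false-positive chance of about 20%. The documents do not support that:

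- The five come from the background rationale, three of them as examples; no outcome or analysis section lists them.
- The 0.05 level for Aim 2 is written only for the caesarean test. Extending it to the others is an inference from the absence of any other level.
- The percentage depends on the number of tests, the event rates, the correlation and the choice between chi-square and Fisher's test, most of which the plan leaves open.

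**Conclusion.** The concern holds as a matter of specification. Aim 2 has no closed list of outcomes, no deciding test and no error control, and the two outcome lists differ. If each complication is tested at 0.05, the false-positive chance for the aim exceeds that of one test by an amount the plan does not limit.

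For the illustrative five, with no true effect on any of them, mixed assumed rates between 1% and 20%, and latent correlation 0 to 0.6, it is about 16% to 23% for any result and about 8% to 12% for one favouring the OSD. The second figure matters more, since the aim is a reduction. A longer list raises both; Fisher's test throughout, uniformly very rare events or strong correlation lowers them. It would be wrong to infer that the trial's main conclusion is affected: the Aim 1 error rate is unchanged. This is a cheap and worthwhile improvement to a secondary aim.

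**What to change.** Add to Aim 2 in I.1.3.4:

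> One test decides Aim 2: caesarean section, the outcome used for the 86% power statement, compared between arms at two-sided 0.05. All other complications are reported by arm as counts, risk difference and 95% confidence interval, without a significance claim.

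Make the secondary outcome in I.1.1 and in I.1.3.2 match: caesarean section as the Aim 2 outcome, with other complications as descriptive outcomes.

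The cost is one statement in the analysis section and two aligned lists, with no change to sample size, procedures or data collection. The downside is that an isolated significant result on another complication can no longer be presented as meeting Aim 2.
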